9.12 Safety Measurements

This study will utilize the CTCAE (NCI Common Terminology Criteria for Adverse Events) version 4.0 for AE and SAE reporting. An electronic copy of the CTCAE v.4 can be found at: https://evs.nci.nih.gov/ftp1/CTCAE/CTCAE_4.03_2010-06-14_QuickReference_5x7.pdf

9.12.1 Adverse Events

An adverse event is the appearance or worsening of any undesirable sign, symptom, or medical condition occurring after starting the study drug treatment, even if the event is not considered to be related to the study drug. For the purposes of this study, the terms toxicity and adverse event are used interchangeably. Medical conditions/diseases present before starting on the study drug are only considered adverse events if they worsen after starting study drug. Abnormal laboratory values or test results constitute adverse events only if they induce clinical signs or symptoms, are considered clinically significant, or require therapy

Collection of adverse events will begin following the initial treatment with carvedilol and continue through to the last visit (the second clamp study). Adverse events will be documented in the study source record and recorded in the CRF.

Information about all adverse events, whether volunteered by the subject, discovered by investigator questioning, or detected through physical examination, laboratory test or other means, will be collected and recorded and followed as appropriate.

The occurrence of adverse events should be sought by non-directive questioning of the patient at each visit or phone contact during the study. Adverse events may also be detected when they are volunteered by the patient during or between visits or through physical examination, laboratory test or other assessments. As much as possible, each adverse event should be evaluated to determine:

1. The severity grade based on CTCAE v.4
2. The relationship of the event to the study drug(s): definite, probable, possible, unlikely, not related.
3. The duration: start and end dates, or continuing at final follow-up visit
4. Action taken: (e.g. study drug interrupted or dosage modified, concomitant medication taken, non-drug therapy, hospitalization, or no action taken)
5. Whether the event constitutes a Serious Adverse Event (SAE)

All adverse events will be treated appropriately. Such treatment may include changes in study drug treatment as listed in the dose modification section of this protocol (see section 7 for guidance). Once an adverse event is detected, it should be followed until its resolution and assessment should be made at each visit (or more frequently, if necessary) of any changes in severity, the suspected relationship to the study drug, the interventions required to treat it, and the outcome.

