2 BACKGROUND

Hypoglycemia elicits a multifaceted hormonal response that helps restore glycemic levels to normal. As blood glucose levels start to fall, insulin secretion ceases. At the top of this hierarchy of counterregulatory responses are glucagon and epinephrine which are the two principal hormones that act rapidly to increase glucose production and inhibit glucose utilization to raise plasma glucose levels back to normal¹. In cases of prolonged and/or more severe hypoglycemia, growth hormone and cortisol are mobilized to stimulate the synthesis of gluconeogenic enzymes and inhibit glucose utilization². In non-diabetic individuals, glucagon and epinephrine are usually very effective and the latter responses are rarely required in the acute situation. In contrast, impaired glucose counterregulation presents itself in longstanding diabetes and with antecedent hypoglycemia³. Within the first five years after the onset of Type 1 diabetes (T1DM), the primary defense against hypoglycemia, the release of glucagon, either becomes significantly attenuated or is completely absent in diabetic patients and this impairment appears to be specific for the stimulus of hypoglycemia^{4,5}. Hence, patients with diabetes primarily depend on the release of epinephrine as their main defense against hypoglycemia. Unfortunately, with longer duration of diabetes and especially with poor glycemic control, epinephrine secretion is also compromised, making these patients even more vulnerable to the threat of hypoglycemia⁵⁻⁷. In patients with diabetes, hypoglycemia arises from the interplay of a relative excess of exogenous insulin and defective glucose counterregulation and it remains a limiting factor in attaining proper glycemic management. Both the Diabetes Control and Complications Trial (DCCT) conducted in Type 1 patients⁸ and the United Kingdom Prospective Diabetes Study (UKPDS) conducted in Type 2 patients⁹, have established the importance of maintaining good glucose control over a lifetime of diabetes to avoid cardiovascular, renal and neurological complications. However, lowering glycemic goals for diabetic patients increases their risk for hypoglycemia exposure. According to the DCCT, T1DM patients put on intensive insulin therapy, though having improved outcomes for diabetic complications, are at a 3-fold higher risk of experiencing severe hypoglycemia compared to those on conventional insulin therapy¹⁰. Moreover, recent antecedent hypoglycemia reduces autonomic (epinephrine) and symptomatic (which normally

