3 DRUG INFORMATION

In this study, carvedilol will be administered twice daily to the intervention group. Carvedilol is currently approved by the FDA for indications that are unrelated to the current study. The following is a summary of the FDA label for carvedilol which can be found in the following link: https://www.accessdata.fda.gov/drugsatfda_docs/label/2005/020297s013lbl.pdf.

Carvedilol is a white to off-white powder with a molecular weight of 406.5 and a molecular formula of $C_{24}H_{26}N_2O_4$. Carvedilol is rapidly and extensively absorbed following oral administration, with absolute bioavailability of approximately 25% to 35% due to a significant degree of first-pass metabolism.

Following oral administration, the apparent mean terminal elimination half-life of carvedilol generally ranges from 7 to 10 hours. Plasma concentrations achieved are proportional to the oral dose administered. Carvedilol is more than 98% bound to plasma proteins, primarily with albumin. The plasma-protein binding is independent of concentration over the therapeutic range. Carvedilol is extensively metabolized. Less than 2% of the dose is excreted unchanged in the urine. The oxidative metabolites are further metabolized by conjugation via glucuronidation and sulfation. The metabolites of carvedilol are excreted primarily via the bile into the feces. Plasma concentrations of the active metabolites are about one-tenth of those observed for carvedilol and have pharmacokinetics similar to the parent. The primary P450 enzymes responsible for the metabolism of carvedilol in human liver microsomes are CYP2D6 and CYP2C9 and to a lesser extent CYP3A4, 2C19, 1A2, and 2E1. Since carvedilol undergoes substantial oxidative metabolism, the metabolism and pharmacokinetics of carvedilol may be affected by induction or inhibition of cytochrome P450 enzymes such as Rifampin, Cimetidine and Digoxin.

Indications for use of carvedilol are congestive heart failure, left ventricular dysfunction following myocardial infarction and hypertension. It is contraindicated in patients with bronchial asthma or related

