8 STUDY CALENDAR

Period	Screening	Treatment Period			
		Intervention Phase (4 weeks)			
		Baseline CGM	1 st Hypoglycemic Clamp Study	Follow-Up	2 nd Hypoglycemic Clamp Study
Visit No.	1	2	3	4	5
Week ¹	-5 to -2	-2	0	1-2	4
Assessments					
Informed consent	X				
Inclusion/Exclusion criteria	X				
Demographics	X				
Vital signs	X		X	X	X
Physical Examination	X				
Pregnancy Test	X	X	X		X
ECG	X		X		X
Hematology/Chemistry/Urinalysis ²	X				
AE Assessment		X	X	X	X
Concomitant Medications	X	X	X	X	X
CGM and Glucometer		X ³	X	X	X ³
Fear Survey			X	X	X
Hypoglycemia Awareness Survey	X			X	X
Overnight Hospital Admission			X		X
Investigational Drug Treatment			X ⁴	X	X ⁴
Primary Objective Assessment			X		X
Secondary Objective Assessment			X		X

1. All screening procedures should be completed within 4 weeks of study enrollment (Visit 1), with the exception of laboratory tests which must be completed within 2 weeks, and pregnancy test which must be completed within 48 hours of screening (Visit 1). All visits within the “Treatment Period”, except the 2nd hypoglycemic clamp study, should occur within \pm 3 days of target date. The 2nd hypoglycemia clamp may be postponed up to 7 days due to hypoglycemia prior to the clamp study.
2. Hematology labs include CGC with differential and platelets; Chemistry labs include c-peptide, HbA1c, Hemoglobin, Albumin, Alkaline Phosphatase, Aspartate Aminotransferase, Alanine Aminotransferase, Total Bilirubin, Creatinine, Glucose, Potassium, TSH, Sodium and Urea Nitrogen; Urinalysis is a dipstick urinalysis including Protein, Hemoglobin and Glucose

3. The CGM is placed after enrollment and until the completion of the second hypoglycemic clamp study. Bayer Contour Next EZ[®] glucometer will be provided to participant and they will be required to use it to monitor their blood glucose and to calibrate the blinded CGMs.
4. The investigational drug treatment is to be started after the first hypoglycemic clamp study and completed on the day prior to the second hypoglycemic clamp study.

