9.11 Efficacy Measurements

On all treatment visit days, dosing will occur after all of the safety and efficacy assessments that are scheduled for that particular visit have been completed.

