9.12.4 Reporting of Pregnancy

Although pregnancy is not considered an adverse event, it is the responsibility of the PI or their designee to report any pregnancy or lactation in a subject, including the pregnancy of a male subjects' female partner as an SAE. Pregnancies or lactation that occurs during the course of the trial or within 30 days of completing the trial or starting another new therapy, whichever is earlier, must be reported to the IRB, FDA, and the funding sponsor as applicable. *All subjects and female partners who become pregnant must be followed to the completion/termination of the pregnancy.* Pregnancy outcomes of spontaneous abortion, missed abortion, fetal death, intrauterine death, miscarriage and stillbirth must be reported as serious events.

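### Adverse event collection closes at the second clamp, about a day after the last dose and on the day of a new induced hypoglycemia, with no contact scheduled afterwards

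*Combined protocol and SAP*

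**What the plan says.** Section 9.12.1 sets the collection window. It opens with the first treatment and is to "continue through to the last visit (the second clamp study"). For an event already detected, the same section says "it should be followed until its resolution and assessment should be made at each visit", or more often if needed.

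The section 8 calendar ends at Visit 5, the second clamp. No later visit or call appears there or in section 9. Footnote 4 says that drug is "completed on the day prior to the second hypoglycemic clamp study"; no clock time is given. Section 9.11 reads differently: "On all treatment visit days, dosing will occur after all of the safety and efficacy assessments" scheduled for that visit. The calendar also carries a drug mark at Visit 5, which refers to footnote 4.

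Section 9.10 describes the first clamp, in which glucose is lowered in steps to 45 mg/dl, and states that the second is identical. After the first clamp the participant receives a hypoglycemia log book and returns 7-14 days into treatment.

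Section 3 reports that "the apparent mean terminal elimination half-life of carvedilol generally ranges from 7 to 10 hours". Section 2 states that recent hypoglycemia weakens the hormone and symptom responses to later episodes. Section 9.12.4 makes pregnancy reportable if it occurs "within 30 days of completing the trial" or before another new therapy starts, whichever is earlier.

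**The concern.** The window closes on a day when two exposures are recent. Carvedilol has been stopped for about a day, and glucose has just been taken to 45 mg/dl in patients whom section 6.3 describes as being at raised risk of hypoglycemia. By the protocol's own background, such an episode can make the next one harder to notice. A participant who goes home and has a severe low the next day is not asked about it by anyone.

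What is at stake is the completeness of the safety record. Hypoglycemia is both the condition under study and the main safety question, and section 9.13 states that there are no halting rules. With 7 participants per arm, one severe episode is 1/7 = 14% of an arm, so a single missed event would change how an arm's safety reads. Passive reporting is also weak for this event, because these patients were selected for not recognizing hypoglycemia.

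**Working it through.** The plan gives no figure for post-treatment follow-up that could be reproduced. The check has two parts.

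**Residual drug when collection closes**

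Inputs:
- Half-life 7 to 10 h (section 3).
- Last dose on the day before the clamp (section 8, footnote 4). The hour is not stated, so I assume 12 to 24 h from last dose to the end of the clamp visit.
- Carvedilol participants: 7 + 7 = 14 of 21 (section 4.3). The 7 on placebo have no residual drug.

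Formula, assuming first-order elimination: fraction remaining = 0.5^(t / half-life).

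| Hours since last dose | Half-life 7 h | Half-life 10 h |
|---|---|---|
| 12 | 0.5^(12/7) = 0.305 | 0.5^(12/10) = 0.435 |
| 18 | 0.5^(18/7) = 0.168 | 0.5^(18/10) = 0.287 |
| 24 | 0.5^(24/7) = 0.093 | 0.5^(24/10) = 0.189 |

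So about 9% to 44% remains. Five half-lives, a common convention that the documents do not use, take 5 × 7 = 35 h to 5 × 10 = 50 h from the last dose. The part of that interval falling after the visit is 35 − 24 = 11 h at the least and 50 − 12 = 38 h at the most.

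If section 9.11 were followed literally and a dose were taken after the second clamp, the whole 35-50 h would fall after the visit. A call at 3 days (72 h) lies beyond 50 h on either reading.

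**What follows each clamp**

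| | After first clamp | After second clamp |
|---|---|---|
| Glucose recovery and meal in clinic | yes | yes (identical procedure) |
| Log book in use | yes | not stated |
| Scheduled visit or call | visit at 7-14 days | none |
| New events after discharge | solicited at that visit | only if volunteered |

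Section 9.10 also delays a clamp by one week if low glucose is seen in the 24 h before it. That rule protects the clamp measurement, but it rests on the same idea of carry-over from a recent low. Section 2 gives no duration for the blunting, so the documents do not fix how long follow-up after the second clamp would have to be.

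**The case against.** Much can be said for the plan as written.

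- Recovery takes place in the clinic, with glucose restored and a meal given. The hours straight after the clamp are therefore observed.
- Section 7.2 gives every participant a telephone number, and section 9.12.1 accepts volunteered reports.
- Detected events are followed to resolution, more often than at visits if needed, and may be recorded as continuing at the final visit.
- Sections 9.12.2 and 9.12.3 cover all serious events and set no end date. Their reporting clocks start when the investigator learns of the event.
- The remaining drug is a declining remnant of low doses, after four weeks of monitored exposure.

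All of this stands, and it rules out several stronger readings. A reader might infer that the protocol marks a post-clamp risk period and then leaves it unobserved. It does not: the half-life is part of a label summary, and the 24-hour rule serves the measurement. A reader might infer that follow-up to resolution and pregnancy reporting are impossible. Neither needs a visit fixed in advance. A reader might infer that a later serious event would go unreported. It would be reportable once known.

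A reader might also object to the monitor being removed, since "The CGM is placed after enrollment and until the completion of the second hypoglycemic clamp study". But the monitor is blinded and its data serve a secondary efficacy comparison, so it gives the participant no alert.

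What the objection does not reach is a new event after discharge that nobody asks about. Follow-up to resolution applies only to an event already detected, and a telephone number works only if the participant uses it.

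**Conclusion.** The concern holds in a limited form. Solicited collection stops at the second clamp, and no contact is scheduled after it for any of the 21 participants. New events after discharge, whether they follow the induced low or fall in the elimination tail, are captured only if volunteered. About 9-44% of the drug remains at that point in the 14 carvedilol participants, given first-order elimination and the assumed 12-24 h since the last dose.

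The size of any under-ascertainment cannot be computed, because the documents give no event rate after a clamp or after stopping drug. It might be inferred that the trial's safety conclusion will be too favourable to carvedilol. That is not shown: all arms undergo the same clamps and the same closing date, and section 10 specifies no safety analysis. It might also be inferred that adverse events should be collected for 30 days. That figure belongs to the pregnancy clause, where it is an upper limit, and neither the half-life nor the text on antecedent hypoglycemia supports it.

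**What to change.** In section 9.12.1, replace the end of the window with wording such as: *Adverse events and serious adverse events are collected until a scheduled telephone contact about 3 days after the second clamp.* Add that contact as a column in the section 8 calendar, and have participants keep the hypoglycemia log book until the call. Use the call to remind participants of the pregnancy reporting duty in section 9.12.4 (up to 30 days or the start of another therapy, whichever comes first). Section 9.12.1 already foresees questioning by telephone, so no new method is needed.

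Separately, section 9.11 and the Visit 5 drug mark must be reconciled with footnote 4, so that the time of the last dose is unambiguous.

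The cost is one short call per participant, 21 in all, made by existing staff, plus wording changes to the protocol and calendar. Each participant's study end moves about 3 days later. No visit or procedure is added.

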9.12.2 Serious Adverse Events

Information about all serious adverse events will be documented in the study source record and recorded in the CRF. A serious adverse event is an undesirable sign, symptom or medical condition which:

- Is fatal or life-threatening
- Results in persistent or significant disability or incapacity
- Requires inpatient hospitalization or prolongation of existing hospitalization (unless the hospitalization is for routine treatment or monitoring of the studied indication, or elective or pre-planned treatment of a pre-existing condition unrelated to the indication under study)
- Causes a congenital anomaly or birth defect
- Is medically significant, i.e., defined as an event that jeopardizes the subject or may require medical or surgical intervention to prevent one of the outcomes listed above

Toxicities which fall within the definitions listed above must be documented as an SAE regardless if they are felt to be treatment related or not.

9.12.3 Serious Adverse Event Reporting Requirements

An event determined to be an SAE must be reported to the IRB and the FDA according to the requirements described below:

IRB Notification:

The PI is responsible to report SAEs that meet the definition of an Unanticipated Problem through the ERICA system *within 10 working days* from the time the investigator learns of the event. An Unanticipated Problem is an event that is:

- **Unexpected** – unforeseen by the investigator in terms of nature, severity, or frequency, given the research procedures and the subject population being studied
- **Related or Probably Related** – determined by the investigator to be related or probably related to participation in the clinical trial
- **Greater Risk** – the severity or scope of the event suggests that the research places subjects or others at greater risk of harm than was previously known or recognized

FDA Notification:

FDA regulations require the PI to report any serious and unexpected adverse event for which there is a reasonable possibility that the drug caused the event. Fatal or life-threatening events that meet these criteria must be reported *within 7 calendar days* from the time the investigator learns of the event. All other reportable events must be reported *within 15 calendar days*. The SAE should be reported on a MedWatch form and submitted as an amendment to the IND. For studies without an IND, the MedWatch report should be submitted to the FDA through the voluntary reporting method.

9.12.4 Reporting of Pregnancy

Although pregnancy is not considered an adverse event, it is the responsibility of the PI or their designee to report any pregnancy or lactation in a subject, including the pregnancy of a male subjects' female partner as an SAE. Pregnancies or lactation that occurs during the course of the trial or within 30 days of completing the trial or starting another new therapy, whichever is earlier, must be reported to the IRB, FDA, and the funding sponsor as applicable. *All subjects and female partners who become pregnant must be followed to the completion/termination of the pregnancy.* Pregnancy outcomes of spontaneous abortion, missed abortion, fetal death, intrauterine death, miscarriage and stillbirth must be reported as serious events.

9.13 Study Halting Rules

There are no study halting rules for this study.

10 STATISTICAL CONSIDERATIONS

A total of 21 T1DM patients with impaired awareness of hypoglycemia will be sought for this study. For the dose response study, we plan to enroll 21 of these patients who will be randomized to either placebo (N=7) or carvedilol (2.5mg or 3.125mg twice daily; N=7 each).

In estimating the appropriate sample sizes required to yield adequate statistical power, assuming a Type II error rate (β) of no more than 20% for a given test and a Type I error rate of $\alpha=5\%$, we used the following: $\text{Power} \geq 1-\beta = 1-0.2 = 0.8$

Treatment effects will be analyzed using one- or two-way analysis of variance (ANOVA) for independent or repeated measures as appropriate, followed by suitable *post-hoc* analysis. Analyses will be performed using the GraphPad Prism[®] or SAS[®] suite of software. We will use a significance level of $\alpha<0.05$.

Primary variables:

- a) Symptom Scores (autonomous, neuroglycopenic and other symptoms of hypoglycemia)
- b) Counterregulatory Hormone Responses (glucagon, epinephrine, norepinephrine, growth hormone and cortisol levels)

Secondary variables:

- a) Frequency of hypoglycemia assessed by CGM.

The primary and secondary variables will be analyzed by the statistical approaches mentioned above.

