Note: This document is signed electronically through submission and approval by the Principal Investigator in the University of Utah IRB Electronic Research Integrity and Compliance Administration (ERICA) system.

STUDY SUMMARY

Title	The Use of Low-Dose Carvedilol to Improve Hypoglycemia Awareness in Patients with T1DM
Short Title	Carvedilol for Hypoglycemia Unawareness
Protocol Number	IRB #: 00108879
IND	Exemption Approved
Phase	Phase II
Design	Double-blinded, randomized, placebo-controlled study.
Study Duration	From Fall 2018 to Spring 2020
Study Center(s)	University of Utah Health
Objectives	The aim of the study is to investigate whether low-dose carvedilol treatment can improve hypoglycemia awareness and the counterregulatory hormone responses to hypoglycemia in Type 1 diabetic patients with impaired awareness of hypoglycemia.
Number of Subjects	A total of 21 Type 1 diabetic patients with impaired awareness of hypoglycemia will be recruited for the study – 7 subjects will be treated with placebo and 7 subjects will be treated with one of two different doses of carvedilol (2.5 or 3.125mg).
Diagnosis and Main Eligibility Criteria	
Patients with Type 1 diabetes and hypoglycemia unawareness will be included in this study.
 
Inclusion criteria:
 
 • Type 1 diabetes of >5yrs duration • >18yrs of age • Impaired hypoglycemia awareness/unawareness assessed by validated questionnaires. • Intensive insulin treatment as defined by multiple daily insulin injections (3 or more) or insulin pump therapy. • Negative pregnancy test. • Signed informed consent. 
Exclusion Criteria:
 
 • Major medical disorders (including liver disease, cardiovascular disease, kidney disease, COPD, asthma, active malignancy and HIV).

	
 • Overt diabetic complications (neuropathy, nephropathy, retinopathy). • Anemia. • Current or recent use of beta-blocker therapy. • Use of diuretics. • Allergies or contraindications to beta-blockers or heparin. • Pregnant. • Use of benzodiazepines. • Alcohol, drug or medication abuse. • Frequent use of acetaminophen.

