Study Product, Dose, Route, Regimen	Hypoglycemia unaware T1DM subjects will be randomly segregated into one of two therapeutic treatment groups: Placebo or Carvedilol. Carvedilol will be administered orally at either 2.5mg or 3.125mg twice daily. Likewise, the placebo drug will also be administered orally twice daily.
Duration of Administration	4 weeks
Reference Therapy	Placebo
Statistical Methodology	Treatment effects will be analyzed using one- or two-way analysis of variance (ANOVA) for independent or repeated measures as appropriate, followed by suitable post-hoc analysis. Analyses will be performed using the GraphPad Prism® or SAS® suite of software.

STUDY SCHEMA

[figure not shown]

Figure 1: Schematic of the study design.

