4 STUDY DESIGN

4.1 Description

The current study will be a double-blinded, placebo-controlled study in which Type 1 diabetic patients with hypoglycemia unawareness are randomized to either 1) placebo treatment, 2) 2.5mg carvedilol twice daily or 3) 3.125mg carvedilol twice daily. After enrollment, the participants will be placed on (blinded) CGM monitoring which will be continued until the end of the study. Additionally, participants will be provided with a glucometer to measure their blood glucose and for calibrating the CGMs during the study. One week after CGM placement, the participants will undergo the first hypoglycemic clamp study to obtain baseline measures of hypoglycemia frequency (from downloaded CGM data), hypoglycemia awareness scores and hormone responses. Following the initial clamp procedure, the patients will be randomized to either 4 weeks use of carvedilol or placebo. After the 4 weeks of treatment, the participants will undergo a second hypoglycemic clamp session. Patients will be hospitalized the night before each clamp study to ensure stable glucose levels.

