4.3 Number of Subjects

21 Type 1 diabetic patients with hypoglycemia unawareness will be recruited for the study. The 21 T1DM patients will be randomly allocated to one of the following treatments: 1) placebo (N=7), 2) 2.5mg carvedilol twice daily (N=7) or 3) 3.125mg carvedilol twice daily (N=7). Placebo will be taken twice daily.

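### Section 10 randomises 7/7/7 and calls this a dose-response study but names no primary between-group contrast, although the objective is carvedilol versus placebo and the doses differ by only 25%

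*Combined protocol and SAP*

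**What the plan says.** **Arms.** Section 4.1 says patients "are randomized to either 1) placebo treatment, 2) 2.5mg carvedilol twice daily or 3) 3.125mg carvedilol twice daily", and Section 4.3 gives "1) placebo (N=7), 2) 2.5mg carvedilol twice daily (N=7) or 3) 3.125mg carvedilol twice daily (N=7"). Section 10 repeats the 7/7/7 split and adds the dose-response label: "For the dose response study, we plan to enroll 21 of these patients who will be randomized to either placebo (N=7) or carvedilol".

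The Study Summary is less clear. Its regimen row says patients are "randomly segregated into one of two therapeutic treatment groups: Placebo or Carvedilol", and then names both doses: "Carvedilol will be administered orally at either 2.5mg or 3.125mg twice daily". Its number-of-subjects row reads "7 subjects will be treated with placebo and 7 subjects will be treated with one of two different doses of carvedilol (2.5 or 3.125mg"), which adds up to the stated 21 only if it means 7 per dose. Later in Section 4.1, after the three arms are listed, randomisation is again described as carvedilol or placebo.

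**Question.** The Summary objective, Section 1.1 and Section 9.11.1 all ask about carvedilol treatment without distinguishing doses. Section 9.11.1 compares it with the patients' own baseline and/or with the placebo group. Section 4.2 adds a dose-related goal: to use the smallest dose that works.

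**Analysis.** Section 10 plans one- or two-way ANOVA, independent or repeated measures as fits, then a suitable post-hoc analysis, at 5%. It names no pooled contrast, dose-versus-placebo contrast, trend test or order of testing.

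**Exposure.** Section 3 says of carvedilol: "Plasma concentrations achieved are proportional to the oral dose administered".

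**The concern.** With three arms and one two-group question, the analyst must decide how the 14 carvedilol patients enter the comparison with placebo. Pooling them, testing each dose against placebo, relying on the three-group F test, or fitting a trend would all comply with Section 10 as written. With 7 per arm these routes can easily give different answers, and the choice could be made after the data are seen.

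Two things are at stake. The first is power for the stated objective, since the routes differ appreciably in what they can detect. The second is interpretation. The dose-response label and the goal in Section 4.2 suggest that the trial will say something about dose, although the arms are close in dose and very small.

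**Working it through.** **Inputs from the documents.** Arms of 7, 7 and 7 (Sections 4.3 and 10); doses of 2.5 and 3.125 mg twice daily; alpha 5%; power at least 80% for an unnamed test (Section 10).

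**Assumptions.** Effects are in units of the between-patient SD of the analysed measure, because no effect size or SD is given. Tests are two-sided, because sidedness is not stated. The error term comes from the three-group model, with 21 − 3 = 18 degrees of freedom and critical t = 2.101 (2.445 with Bonferroni for two dose comparisons). There is no dropout.

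**The plan's own figure.** N = 21 with 80% power cannot be reproduced, because the endpoint, contrast, effect and SD are all missing. Working backwards by the normal approximation, 7 v 7 fits an effect of (1.960 + 0.842) × √(2/7) = 1.50 SD.

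**Standard errors (in SD).**
- Pooled, 14 v 7: √(1/14 + 1/7) = 0.463.
- One dose, 7 v 7: √(1/7 + 1/7) = 0.535.
- Ratio: 0.463/0.535 = 0.866.

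**Noncentrality.** For a t contrast it is effect/SE. For the F test it is λ = 7 × Σ(group mean − overall mean)², with 2 and 18 degrees of freedom.
- Both doses at 1.0 SD: pooled 1.0/0.463 = 2.16; one dose 1.0/0.535 = 1.87; means 0, 1, 1 give λ = 7 × 0.667 = 4.67.
- Effects of 0.8 and 1.0 SD, proportional to dose (2.5/3.125 = 0.8): pooled effect 0.9, so 0.9/0.463 = 1.94; single doses 0.8/0.535 = 1.50 and 1.87; means 0, 0.8, 1.0 give λ = 7 × 0.56 = 3.92.

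**Results (noncentral t and F).**

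| Route | Detectable at 80% power | Power, both doses 1.0 SD | Power, 0.8 and 1.0 SD |
|---|---|---|---|
| Pooled 14 v 7 | 1.37 SD | 53% | 45% |
| Three-group F test | 1.57 SD (equal effects) | 41% | 35% |
| One dose v placebo, unadjusted | 1.58 SD | 43% | 29% (lower), 43% (higher) |
| One dose v placebo, Bonferroni | 1.77 SD | 31% | 20% (lower), 31% (higher) |

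**Dose against dose.** 3.125/2.5 = 1.25, so by Section 3 expected exposure differs by 25%. If effect is also proportional to dose (an assumption), the gap is 20% of the higher dose's effect: 0.2 SD if that effect is 1.0 SD, and 0.4 SD if it is 2.0 SD. Power for 7 v 7 is then about 5% to 11% for a significant result in the right direction. Reaching 80% would take about 2 × (1.960 + 0.842)²/0.2² ≈ 393 per arm for the 0.2 SD gap, or about 99 per arm for 0.4 SD. The 95% interval for the dose difference would have a half-width of 2.101 × 0.535 = 1.12 SD.

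**The case against.** A reader might infer that the plan commits to two 7 v 7 comparisons and so leaves half the carvedilol patients out of each test. It does not. Section 10 defines no post-hoc test, and a three-group F test uses all 21 patients. Post-hoc contrasts from that model would also use its 18 error degrees of freedom rather than the 12 of an isolated 7 v 7 t-test. The defect is an undefined contrast, not a badly chosen one.

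Nor does the two-group wording in the Summary work against pooling. Together with Section 9.11.1, it points towards carvedilol as a whole against placebo. That is a hint and does not pre-specify an analysis.

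A reader might also infer that a dose-response test is planned and underpowered. The label appears in Section 10, but no trend or dose-versus-dose test is described. The 5% to 11% therefore shows what the trial could say about dose; it is not the power of a planned analysis.

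Three further points stand in part:
- The gain from pooling depends on the comparison. With effects of 0.8 and 1.0 SD, the pooled contrast has 45% power against 43% for the higher dose alone, unadjusted. The advantage is clear only against the lower dose, the F test or the adjusted comparisons.
- Section 4.2 has a dose goal that needs per-dose information, so the arms should still be reported separately.
- The conflict over the number of groups is mainly editorial, because Sections 4.1, 4.3 and 10 agree on three arms of 7.

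**Conclusion.** The point holds as an unspecified primary contrast. Section 10 leaves open how 14 carvedilol patients on two doses are compared with 7 on placebo, while the objective treats carvedilol as one treatment. Pooling within the three-group model lowers the detectable effect to 1.37 SD, from 1.57 SD for the F test and 1.58 SD for a single dose (1.77 SD adjusted). At equal effects of 1.0 SD it gives about 10 to 12 points more power than the F test or an unadjusted single-dose test.

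These sizes rest on an assumed effect and SD, two-sided testing and complete data. Baseline adjustment would lower the raw difference needed for every route alike and would not change their order. The order does rest on the two doses having similar effects, which is plausible for exposures 25% apart but is not shown in the documents. The pooled contrast does not rescue power in general: 53% at 1.0 SD is still low. Nor does it settle multiplicity across the several symptom groupings and five hormones.

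**What to change.** In Section 10:
- Name pooled carvedilol (n=14) against placebo (n=7) as the primary between-group contrast for each primary variable, estimated within the three-group model so that the error term still comes from all three arms.
- Report each dose against placebo, and dose against dose, descriptively with confidence intervals.
- Drop the dose-response label, or qualify it. State that with 7 per arm the trial cannot separate the two doses, and that this limits what it can say about the Section 4.2 goal.

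Elsewhere, reconcile the two-group wording in the Summary's regimen row and at the end of Section 4.1 with the three arms in Sections 4.1, 4.3 and 10. Reword the Summary's number-of-subjects row so that 7 per dose is explicit.

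The cost is wording. No dose, arm or sample size changes. The downside is that the pooled estimate averages over two doses and dose-specific conclusions become descriptive. If the sponsor prefers another contrast, it should be named before unblinding with its detectable effect beside it.
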